IDH1/2 mutations in all grades and sub-types of gliomas are presented in Fig. 14, which is taken from a comprehensive review on this subject ⁴⁹. Another factor is likely to have even further reduced the proportion of IDH1/2-mutant tumors that have been tested in clinical trials with PARP inhibitors: most studies specifically excluded secondary GB and/or tumors with features suggestive of components arising from lower grade gliomas. For example, a Phase II/III randomized Alliance trial (A071102; NCT02152982) is

ABTC # 1801

NCI # ABTC-1801

PI: [name]

testing the efficacy of the PARP inhibitor, veliparib, in combination with adjuvant temozolomide in newly diagnosed GB, but it specifically excludes GBs with oligodendroglial features with a 1p19q co-deletion; these tumors commonly harbor IDH1 mutations ⁵⁰. As another example, the aforementioned Oparatic Trial in recurrent GB specifically excludes secondary GB ⁵¹. Collectively, these findings suggest that the target glioma population in whom PARP inhibitors have been tested thus far may not have been the optimal experimental cohort. Instead, an ideal group would be composed of patients with IDH1/2-mutant gliomas, and the proposed trial will test this specific group of patients.

Since the initial concept for this trial was developed, additional information regarding the combination of pamiparib (BGB-290) and TMZ has become available. BGB-290-104, a phase I study for patients with first recurrence of glioblastoma, utilized our proposed dose level 1 of pamiparib (BGB-290) 60 mg twice daily and TMZ 40 mg Days 1-21 every 28 days and found this combination exceeded MTD because of neutropenia and thrombocytopenia. Similarly, BGB-290-103, a solid tumor study using the same pamiparib (BGB-290) schedule with TMZ 40 mg daily, noted excessive hematologic toxicity. Both of these studies have de-escalated TMZ to 20 mg daily.

Pre-clinical data supporting the activity of the PARP inhibitor Pamiparib (BGB-290)

As presented above, we have already confirmed that pamiparib (BGB-290) is active against IDH1/2-mutant versus WT cells. However, pamiparib (BGB-290) also has

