4.1.1 Dose Finding

Pamiparib (BGB-290) will be given at 60 mg BID at each dose/schedule; the dose of TMZ will be de-escalated/changing the treatment schedule, as shown in the table below if necessary:

Dose Level	Pamiparib (BGB-290)	Temozolomide Dose/Schedule
1 (starting dose)	60 mg BID	20 mg QD Days 1-28
-1	60 mg BID	20 mg QD Days 1-21
-2	60 mg BID	20 mg QD Days 1-14
-3	60 mg BID	20 mg QD Days 1-7

Phase I dose/schedule de-escalation

*Pamiparib (BGB-290) will be dose reduced only after discussion with Study Chair

The standard 3+3 design will be used for dose finding. Three patients will be enrolled per dose/schedule cohort. If no DLTs are observed in the first 3 patients at Dose Level 1, 3 additional patients will be enrolled at Dose Level 1 before pursuing Phase II of the protocol. If 1/3 of the patients develops a DLT during the first 4 weeks of treatment beginning from the first dose of pamiparib (BGB-290), Dose/Schedule Level 1 (or any subsequent dose/schedule level) will be expanded by 3 additional patients at the same dose/schedule level. The 3 additional patients must be followed for at least 4 weeks and toxicity evaluated before continuing.

Number of Patients with DLT at a Given Dose/Schedule	Decision Rule
0 out of 3	Enter 3 more patients at the same dose/schedule
1 out of 3	Enter 3 more patients at the same dose/schedule
2 out of 6	This is the maximum tolerated dose/schedule
2-3 out of 3, or \geq 3 out of 6	MTD exceeded, enter 3 patients at next lower dose/schedule

Dose-limiting toxicity (DLT) is defined in Section 5.1. No intra-patient dose escalation is allowed. Patients will be evaluable for the cohort if they have completed at least 80% of their expected dose of pamiparib (BGB-290) for the first treatment cycle (28 days). Patients who experience a DLT will be evaluable for the cohort if they have received at least one dose of pamiparib (BGB-290). The toxicity evaluation period is the first 4 weeks of treatment.

The target DLT rate is 33%. If the MTD is not reached among the pre-specified doses/schedules, the dose for the Phase II portion will be the highest dose/schedule studied for which the DLT rate is \leq 33% in 6 evaluable patients.

ABTC # 1801

NCI # ABTC-1801

PI: [name]

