4.2 Phase II Treatment Plan

The Phase II portion will determine the overall response rate of treatment with pamiparib (BGB-290) combined with TMZ at the recommended Phase II dose in patients with recurrent IDH1/2-mutant gliomas. Patients will be stratified into the following arms:

Arm A

Patients who have experienced recent tumor progression despite prior treatment with TMZ and another alkylating chemotherapy (e.g., BCNU, CCNU or procarbazine) have extremely poor treatment response to subsequent chemotherapies⁵². The primary endpoint for the phase II portion will be response rate based on measurable disease. The study assumes the null hypothesis of response rate at 5% and will accept a 25% response rate as a meaningful treatment effect for pamiparib (BGB-290) with TMZ to treat recurrent/progressive IDH1/2-mutant glioma.

Initially, 15 patients will be enrolled into Arm A. This arm of the trial will be stopped if no response is obtained among the first 15 patients (0/15). Otherwise, the study will continue and 10 additional patients will be enrolled into Arm A.

Arm B

Patients who have experienced recent tumor progression after failure of TMZ or another alkylator and have gone ≥ 12 months since last treatment have a more favorable prognosis and show a range from 0-44% response rate when challenged with an alternative alkylating agent-based regimen ^{60, 61}. The study assumes the null hypothesis of response rate at 30% for the combination regimen and will accept a 50% response rate as a meaningful treatment effect for pamiparib (BGB-290) with TMZ.

Initially, 24 patients will be enrolled into Arm B. This arm of the trial will be stopped if 7 or fewer responses are obtained among the first 24 patients ($\leq 7/24$). Otherwise, the study will continue and 29 additional patients will be enrolled into Arm B.

GBM Arm (exploratory)

Patients with recurrent WHO grade IV GBM that harbor an IDH1/2 mutation will be enrolled into the exploratory arm and also treated with pamiparib (BGB-290) combined with TMZ. Due to the small fraction of patients with these tumors among all recurrent grade IV GBM (~5%), the study will enroll no more than 10 patients into this arm. This group will be analyzed separately from the primary cohorts and their response rates will be reported using descriptive statistics

PI: [name]

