5.0 DOSE MODIFICATION FOR TOXICITY

5.1 Dose Limiting Toxicity (DLT)

A DLT is defined as a clinically significant adverse event or abnormal laboratory value assessed as unrelated to disease progression, intercurrent illness, or concomitant medications and meets any of the criteria below. Any DLT must be a toxicity considered at least possibly related to pamiparib (BGB-290) or TMZ.

ABTC # 1801

NCI # ABTC-1801

PI: [name]

Dose limiting toxicities (treatment related) are defined below. Dose limiting toxicities must have an attribution of possible, probable, or definite to pamiparib (BGB-290) or TMZ. For patients experiencing a DLT, pamiparib (BGB-290) and TMZ will be stopped. If the patient recovers (\leq grade 1 [or tolerable grade 2 for non-hematologic toxicity] or \leq baseline), refer to the Toxicity Management Table below for instruction on whether a dose reduction of TMZ or pamiparib (BGB-290) is required for subsequent doses, or whether pamiparib (BGB-290) and TMZ must be permanently discontinued. Skipped doses will not be made up. If there is any question or confusion concerning a DLT, the treating site should contact the ABTC Central Office to determine patient's DLT status. The ABTC Central Office, with the Study Chair, will make the final decision.

- → Hematological toxicities will be considered dose limiting if any of the following occur and complete blood counts and differentials were obtained according to the mandated schedule (CBC, differential, and platelets drawn twice a week until the ANC ≥ $1500/\mu$ L and platelets ≥100,000/µL): grade 3 or 4 lymphopenia will not be considered a DLT.
 - Grade 4 Neutrophil count decreased (ANC of $< 500/\mu$ L)
 - Grade 4 Platelet count decreased (Platelets $< 25,000/\mu$ L)
 - Grade 3 or 4 Febrile neutropenia
 - Any hematological toxicity that prevents administration of > 80% of the planned TMZ doses for the first cycle

Non-hematological toxicities will be considered dose limiting if any of the following occur:

- Grades 3-4 seizure or intracranial hemorrhage
 - All other grade 3 neurologic toxicity (other than seizure/intracranial hemorrhage) responding *within 3 days* to steroids, anticonvulsants, or electrolyte correction will not be considered dose limiting.
- Grades 3-4 severity with the following exceptions:
 - o except nausea, vomiting, and diarrhea without sufficient prophylaxis *lasting* ≤3 *days*;
 - except alopecia;
 - except grade 3 hyperglycemia;

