11.0 STATISTICAL CONSIDERATIONS

Phase I /Dose Finding

The primary objective of the phase I study is to determine the safety combination treatment of pamiparib (BGB-290) given at a fixed dose level of 60 mg BID with TMZ 20 mg starting at the dose level/schedule 1 (Days 1-28), then subsequently dose level -1 (Days 1-21), dose level -2 (Days 1-14), and dose level -3 (Days 1-7) in patients with recurrent gliomas and IDH1/2 mutations. The standard 3+3 design will be used for dose finding. Three patients will be treated in a dose/schedule cohort and dose deescalation/changing treatment schedule, if required will take a stepwise fashion with expansion to a total of 6 patients at a putative MTD/ or highest safe dose/schedule. The target DLT rate is 33%.

The MTD is defined as the combination regimen that yields a DLT rate less than, or equal to 33%.

The safety evaluation period is 28 days (the first cycle of treatment) for dose escalation decisions. All safety and toxicity will be followed and data will be collected till 90 days after discontinuation of the treatment.

NCI Common Terminology Criteria for Adverse Events (CTCAE) version 5.0 will be used for scoring toxicity and adverse events. The severity and frequency of toxicity will be tabulated by the tested doses using descriptive statistics. The proportions of subjects who experienced grade 3 or above toxicities will be estimated, along with 95% confidence intervals by each type of toxicity.

ABTC # 1801

NCI # ABTC-1801

PI: [name]

The Phase II efficacy study will be warranted after a safe combination regimen is deemed.

Phase II/ Safety and Efficacy

The primary objective of the phase II portion of the study is to estimate treatment effect in terms of tumor radiographic response in two different patient populations independently. One is a poor risk patient population, alkylator resistant/alkylatorrefractory: Arm A. The other is favorable risk patients who had one distant alkylator failure: Arm B.

Primary Endpoint:

The primary endpoint for both Arm A and B is tumor radiographic response (CR+PR) using Response Assessment in Neuro-Oncology (RANO) criteria by measurable disease.

Study Design /Sample Size:

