Arm A: It is a single arm design to test a hypothesis of clinical benefit of 25% radiographic response rate (PR+CR) for patients who failed multiple prior alkylator therapies and are treated with BCB290+TMZ to compare a null of 5%. The sample size estimation is based on a 2-stage design (MiniMax). A total sample size of 25 patients yields 90% statistical power to detect 20% improvement from a null of 5% with a false positive rate at 5%. At the first stage, 15 patients will be enrolled onto the study. The trial will be stopped and the null hypothesis accepted if no response was obtained among the first 15 patients (0/15). Otherwise, the study will continue to stage 2. The probability of early stopping for futility is 0.46 when the null is true and 0.01 when a true response is 25%. Ten additional patients will be enrolled on the second stage of the trial. If 4 or more patients out of the 25 have objective response, the study will reject the null hypothesis to conclude that pamiparib (BGB-290) in combination with TMZ is effective to treat patients with recurrent, alkylator-refractory, and IDH1/2-mutant glioma.

Arm B: It is a single arm study to test a hypothesis of clinical benefit of 50% radiographic response rate (PR+CR) for patients who failed one prior alkylator therapy and are treated with BCB290+TMZ to compare a null of 30%. The sample size estimation is based on a 2-stage design (MiniMax). A total sample size of 53 patients yields 90% statistical power to detect a 20% improvement from a null of 30% with a false positive rate at 5%. At the first stage, 24 patients will be enrolled onto the study. The trial will be stopped and accept the null hypothesis if 7 or fewer responses were obtained among the first 24 patients (\leq 7/24). Otherwise, the study will continue to stage 2. The probability of early stopping for futility is 0.57 when the null is true and 0.03 when a true response is 50%. Twenty-nine additional patients will be enrolled in the second stage of the trial. If 22 or more patients out of the 53 have objective responses, the study will reject the null hypothesis to conclude that pamiparib (BGB-290) in combination with TMZ is effective to treat patients with recurrent, IDH1/2-mutant glioma who failed initial alkylator therapy.

ABTC # 1801

NCI # ABTC-1801

PI: [name]

Additional considerations on first stage/interim analysis:

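### After Phase I the plan sets no study-level toxicity threshold: the numeric stops count responses only, and no DLT count or rate triggers a review

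*Combined protocol and SAP*

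**What the plan says.** **Phase I** has a toxicity rule. Section 4.1.1 sets a 3+3 table with a target DLT rate of 33%, accepts 2 DLTs in 6, and adds that "The toxicity evaluation period is the first 4 weeks of treatment". Section 11 ties that 28-day window to dose-finding decisions and then says "The Phase II efficacy study will be warranted after a safe combination regimen is deemed".

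**Phase II** has response rules. For Arm A, Section 4.2 says "This arm of the trial will be stopped if no response is obtained among the first 15 patients (0/15"); otherwise "10 additional patients will be enrolled into Arm A". For Arm B it says "This arm of the trial will be stopped if 7 or fewer responses are obtained among the first 24 patients", and Section 11 repeats this: "The trial will be stopped and accept the null hypothesis if 7 or fewer responses were obtained among the first 24 patients". Section 11 adds one study-level review, of the FLAIR growth rate with CTEP. It applies only when stage 1 responses are too few, so it can only help an arm continue.

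**The GBM arm** (up to 10) and **the surgical portion** (10, all given the combination after surgery) have no stop.

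**Safety in Phase II** is a secondary endpoint: proportions with 95% confidence intervals, with no threshold and no look time. Sections 5 and 10.1 act on individual patients. Sections 9.3 and 12.4 require SAE reports within 24 hours and quarterly CDUS data to CTEP. Section 12.5 covers GCP and data quality.

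**The concern.** The plan sets its own limit, a DLT rate of 33%, and applies it only to the Phase I cohorts. A 3+3 cohort of 6 estimates that rate very imprecisely, so a regimen above the limit can be carried forward by chance. From then on, an arm with enough responses keeps enrolling at any observed DLT rate, because no written count or rate calls for a study-level look. Patient safety is at stake. So is the secondary objective of confirming safety and tolerability: the plan has no criterion by which Phase II could conclude that the regimen is not tolerable.

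**Working it through.** **1. The plan's own stops reproduce, and they use responses only.** Early stop = P(X1 ≤ r1). Rejection = the sum over x > r1 of P(X1 = x) × P(X2 ≥ r − x).

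| Arm | Rule | Early stop, null / alternative | Exact alpha | Power |
|---|---|---|---|---|
| A (5% v 25%) | 0/15; ≥4/25 | 0.463 / 0.013 (plan 0.46 / 0.01) | 0.034 | 0.901 |
| B (30% v 50%) | ≤7/24; ≥22/53 | 0.565 / 0.032 (plan 0.57 / 0.03) | 0.047 | 0.902 |

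The response designs are sound. The DLT rate does not enter them.

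**2. What the 3+3 rule lets through.** From the Section 4.1.1 table, with true DLT rate p:

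P(accept a level) = P(0/3) × P(≤2/3) + P(1/3) × P(≤1/3)

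- p = 0.33: 0.3008 × 0.9641 + 0.4444 × 0.7452 = 0.621
- p = 0.40: 0.216 × 0.936 + 0.432 × 0.648 = 0.482
- p = 0.50: 0.125 × 0.875 + 0.375 × 0.500 = 0.297

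An observed 2/6 has a Clopper-Pearson 95% interval of 0.043 to 0.777.

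**3. How many patients follow.** Sections 4.2 and 4.3 give 25 + 53 + 10 (GBM) + 10 (surgical) = 98 at most. The enrolment table in Section 3.1 totals 106 = 18 + 78 + 10, which appears to omit the GBM arm and leaves 106 − 18 = 88 after Phase I. If the accepted regimen had a true DLT rate of 40% (assumed), the expected number with a first-cycle DLT would be 0.40 × 98 = 39 (or 0.40 × 88 = 35). At 50% it would be 49 (or 44). No rule would be triggered in either case.

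**4. What a simple rule could detect (illustration).** The assumptions are a Beta(0.66, 1.34) prior, which has mean 0.66/2 = 0.33; looks at n = 6, 12, ..., 96; and outcomes known at each look. After x DLTs in n patients the posterior is Beta(0.66 + x, 1.34 + n − x). A review is triggered when Pr(rate > 0.33) exceeds the cut-off. Trigger probabilities by exact binomial recursion:

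| True DLT rate | Cut-off 0.90 | Cut-off 0.95 |
|---|---|---|
| 20% | 2% | 1% |
| 25% | 6% | 2% |
| 30% | 17% | 8% |
| 33% | 31% | 17% |
| 40% | 74% | 58% |
| 50% | 99% | 98% |

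As written, the plan's trigger probability is 0 in every row. With cut-off 0.90 the boundary is 4/6, 7/12, 9/18, 12/24, 14/30, 16/36, 19/42, 21/48, 23/54, 25/60, 27/66, 30/72, 32/78, 34/84, 36/90, 38/96.

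**5. Delay.** DLTs take 28 days to observe and Section 3.1 expects 2 to 3 patients per month. About 2 to 3 more patients would therefore enrol while each look resolves. The table does not count them.

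**The case against.** The strongest reply is that oversight already exists. SAEs reach the coordinating office within 24 hours and are tracked there. Cumulative data go to CTEP every quarter and to the principal investigator for review. The patient-level rules mandate holds, reductions and discontinuation. This stands. A reader might infer that nobody watches toxicity after Phase I, and the documents do not support that. What is missing is a pre-specified count or rate. Section 12.5 also refers to a monitoring plan that is not among the documents; if it holds such a rule, a cross-reference would close the gap.

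Three other stronger readings also fail:

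- **That 6 patients are the whole safety base.** Section 9.2.1.1 reports 208 patients given the combination by June 2021. Their doses are not given, so this does not replace a rule, but prior knowledge is wider than one cohort.
- **That related studies already showed this regimen to be too toxic.** Section 2.2 says that one of them "found this combination exceeded MTD because of neutropenia and thrombocytopenia", and that the other saw excessive hematologic toxicity. Both results were at TMZ 40 mg, and both studies then went to 20 mg, the daily amount used here.
- **That Phase II patients are more heavily pretreated than Phase I patients.** Section 3.2 allows unlimited prior regimens in Phase I as in Arm A, and Arm B allows at most one.

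A monitoring rule also has a cost at rates the plan accepts, and the table above shows it.

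**Conclusion.** The point holds as a gap in the design; it is not a contradiction in the text. After Phase I no toxicity threshold operates at study level. A dose level with a true DLT rate above the plan's own limit is accepted 48% of the time at 40% and 30% of the time at 50%, and up to 98 patients (or 88) may then follow.

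The acceptance figures assume independent patients and the Section 4.1.1 table applied as printed. The headcount is a maximum that depends on both response arms reaching stage 2. The trigger probabilities rest on an assumed prior, cut-off and look spacing, and on outcomes being known at each look. They show what a rule of this kind can do and do not identify the right boundary. The change is worth making because it is cheap and leads only to a review.

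**What to change.** In Section 11, cross-referenced from 4.2 and 4.3 (or to the monitoring plan if a rule is already there), state that:

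- cycle-1 DLTs as defined in 5.1, on the combination, are counted across Arms A, B and GBM; post-surgical cycles are either pooled or tabulated separately, because those patients have already had single-agent pamiparib;
- after every 6 patients the count is compared with a printed boundary tied to the 33% limit and covering every patient pooled;
- crossing the boundary triggers a study-level safety review with CTEP. Any action on accrual, dose or schedule is left to that review.

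Print the operating characteristics, including at rates the plan accepts. The sponsor chooses the cut-off. Reconcile the 98 from Sections 4.2 and 4.3 with the enrolment table's 106, which implies 88 after Phase I.

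Cost: a paragraph and a table, with no extra patients and no new committee. Section 5.1 already says of DLT questions that "The ABTC Central Office, with the Study Chair, will make the final decision", but counting every Phase II DLT routinely would be new work. Depending on the cut-off, the chance of a review that proves unnecessary is about 8% to 17% at a true rate of 30% and 17% to 31% at 33%.

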4.3 Surgical Portion

Following completion of the Phase I portion, 10 patients with recurrent IDH1/2-mutant glioma (WHO grade II-IV) who are eligible for re-resection at the time of recurrence may be enrolled on a surgical portion of the study (pre-surgical cohort) and will receive pamiparib (BGB-290) 60 mg BID as a single agent for 7 days pre-surgery, including the day of surgery. At surgery fresh tumor tissue will be collected for correlative studies. Following recovery from surgery all patients will receive pamiparib (BGB-290) combined with TMZ post-operatively.

NCI # ABTC-1801

PI: [name]

Patients should begin presurgical treatment with pamiparib (BGB-290) starting 6 days (Day 1) prior to the day of scheduled tumor resection (Day 7). Two additional days of dosing are permitted if unexpected logistical problems delay the surgery.

Doses of pamiparib (BGB-290) should be taken 12 hours apart \pm 2 hours. On the day of surgery, the last pre-surgical dose must be taken 3-6 hours before surgery. The time that the dose is taken on the day of tumor resection must be recorded.

Blood samples for determining the concentration of drug in plasma will be collected from patients at baseline (prior to the first pre-surgical dose), on the day of surgery, immediately before the resection and immediately following the resection; see Section 9.5.2.

The tumor will be resected using neuronavigation or intraoperative MRI, enabling resection of enhancing tumor and resection or biopsy of non-enhancing tumor. Surgical resection of the non-enhancing lesions should be performed only in the non-eloquent areas that show FLAIR changes on MRI. Tissue may be collected from both the

ABTC # 1801

NCI # ABTC-1801

PI: [name]

enhancing core and non-enhancing edge of individual tumors. As a reminder, please refer to the Imaging Core Manual for further imaging requirements and submission information.

The concentration of pamiparib (BGB-290) will be determined in a $0.05-0.10 \text{ cm}^3$ (50-100 mg) section of tumor tissue obtained from a contrast enhancing and non-contrast enhancing region of the tumor. See Section 9.5.2.

Following surgery, all patients will continue with standard post-operative management.

Following recovery from surgical resection*, all patients will receive pamiparib (BGB-290) 60 mg BID in 28-day cycles combined with TMZ at the dose established in the Phase I portion (dose to be determined).

*Adequate recovery from surgical resection includes, but is not limited to, the following:

- No signs or symptoms of infections related to the surgical wound (*i.e.*, increasing erythema or cellulitis of the surrounding area, large amount of drainage, fever)
- Wound edges have healed

Post-operatively, patients must begin treatment within 45 days of surgical resection, and preferably within 3 weeks of the post-operative MRI; if more than 3 weeks elapse after the post-operative MRI, the patient will need a new MRI (please refer to the Imaging Core Manual for more information).

Patients will be followed by routine blood work, general and neurological examination, and MR imaging. See Section 9.1 for schedule.

Patients may continue to receive cycles of pamiparib (BGB-290) until tumor progression, development of unacceptable toxicity, or meeting other criteria for going off treatment (Section 10.1). Patients will be followed for adverse events for at least 30 days after the last dose of pamiparib (BGB-290). All patients will be followed for survival.

